Group G4 – 27 participants who had previously received a full course (2 doses) of an authorized S protein mRNA COVID-19 vaccines, with the second dose administered at least 4 months prior to the enrollment into the study, will receive VBI-2905a at a dose of 5 µg of S protein at Day 1

Group G5 - 27 participants who had previously received a full course of an authorized S protein mRNA COVID-19 vaccines at least 4 months prior to the enrollment into the study, will receive placebo at Day 1

In Phase 1b, the DSMB will review blinded Day 7 safety data after vaccination of the first 10 participants in groups G4 and G5 (previously vaccinated with mRNA COVID-19). Only after the DSMB confirms that safety is acceptable and that stopping rules were not met will the enrollment in the respective study groups continue to its completion. The SSC will review unblinded immunogenicity data 7 days and 28 days after the first vaccinations (Groups G4 and G5). The study will be unblinded following DSMB and SSC review of safety and immunogenicity data collected through Day 56. Study participants will continue with study visits as planned up to 12 months of follow up after the first dose of study vaccine.

Schedule of Events

During the study, there will be a total of 9 visits (Phase 1a and Phase 1b, groups G4 and G5), including the screening visit and 12 months of follow up (see [Table 1](#), and [Table 2](#) below).

During the screening visit participants will provide informed consent, provide samples for SARS-CoV-2 testing (PCR and/or rapid antigen test and for viral variant testing/sequencing) and safety laboratory testing (hematology, biochemistry, urinalysis), provide history of previous COVID-19 vaccination, including type of vaccine and dates of vaccination (Phase 1b), and will be evaluated against study inclusion and exclusion criteria to confirm study eligibility. Eligible participants will proceed to Day 1 to be randomized and receive the study vaccine or placebo.

[figure not shown]

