On the vaccination visits, participants will remain at the site for at least 60 minutes for an evaluation of AEs and vital signs. Participants will be contacted by phone 3 days after each vaccination for a safety follow up call. Diary cards will be distributed to study participants at vaccination visits to record body temperature, local and systemic reactions from day of the vaccination(s) and the next 6 days. Serious AEs (SAEs) and medically-attended AEs (MAAEs) will be recorded throughout the study.

In Phase 1a, participants will visit the study site for dose administration, safety assessments and blood sample collection on Days 1 and 28 (prior to study vaccination) and for safety assessments and blood sample collection on Days 7, 35, 56, 112, 224 and 336.

In Phase 1b, participants will visit the study site for dose administration, safety assessments and blood sample collection on Day 1 for safety assessments and blood sample collection on Days 7, 14, 28, 56, 84, 168 and 336. Study participants will be tested for SARS-CoV-2 infection by PCR or rapid antigen test and surveilled for signs and symptoms of COVID-19 illness throughout the study. Duplicate nasopharyngeal swab samples will be retained for storage and potential sequencing of viral RNA should samples test positive for SARS-CoV-2 infection.

Participants will be followed until the study completion on Day 336. If a subject is lost to follow-up, every effort will be made by the study center personnel to contact the subject and to determine the reason for discontinuation. Measures taken to follow-up will be documented.

Figure 1: Clinical Trial Design

* Not previously vaccinated with any licensed or experimental COVID-19 vaccine and no history of clinical or laboratory diagnosis of SARS-CoV-2 infection or COVID-19 illness

** Received a full course of an authorized mRNA COVID-19 vaccine at least 4 months prior to the study and no history of clinical or laboratory diagnosis of SARS-CoV-2 infection or COVID-19 illness

Table 1: Phase 1a Schedule of Events

Schedule of Events	Screening								Study Period	End-of Study Early D/C	
	1	2	Phone Call	3	4	Phone Call	5	6	7	8	9
Visit											
Study Day	-28 to -1	1	3	7	28	31	35	56	112	224	336
Study Month (28 days)	<-1	0	0.1	0.25	1	1.1	1.25	2	4	8	12
Visit Intervals (Days)	n/a	n/a	±1	+3	±3	±1	±3	±3	±7	±14	±14
Informed consent	●	●									
Inclusion/exclusion criteria	●										
Confirm ongoing eligibility		●									
Demographics	●	●	●								

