4.5 Duration of Study

The total study duration for each vaccinated subject (assuming a screening period of 28 days) is 364 days.

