8.7.1 Unblinding

Blinding will be guaranteed by the preparation of the study vaccine by an unblinded pharmacist or other qualified study-site personnel with primary responsibility for study vaccine preparation.

Participants will be randomly assigned to groups based on a computer-generated randomization schedule prepared before the study by or under the supervision of the sponsor and using the IWRS.

The investigator will not be provided with randomization codes. The codes will be maintained within the IWRS, which has the functionality to allow the investigator to break the blind for an individual participant.

Data that may potentially unblind the study vaccine assignment (e.g., immunogenicity data, study vaccine accountability data, study vaccine allocation, biomarker, or other specific laboratory data) will be handled with special care to ensure that the integrity of the blind is maintained and the potential for bias is minimized. This can include making special provisions, such as segregating the data in question from view by the investigators, clinical team, or others as appropriate until the time of database lock and unblinding.

Each phase of the study will be unblinded after DSMB review of safety data collected through Day 56. Some key personnel of the sponsor, not involved in study operations, may be unblinded at the time of Study Steering Committee analysis. The investigator may in an emergency determine the identity of the intervention by contacting the IWRS. While the responsibility to break the intervention code in emergency situations resides solely with the investigator, it is recommended that the investigator contact the sponsor or its designee if possible, to discuss the particular situation, before breaking the blind.

Telephone contact with the sponsor or its designee will be available 24 hours per day, 7 days per week. In the event the blind is broken, the sponsor must be informed as soon as possible. The date, time, and reason for the unblinding must be documented in the IWRS and in the source document. The documentation received from the IWRS indicating the code break must be retained with the participant's source documents in a secure manner.

Participants who have had their intervention assignment unblinded should continue to return for scheduled evaluations. Participants should not be allowed to receive further study vaccinations and are only to be followed for safety evaluation visits.

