10.1.2 Secondary Endpoints/Outcome Measures

Rate and severity of unsolicited AEs throughout the study

Rate and severity of medically-attended adverse events (MAAEs) throughout the study Rate of serious adverse events (SAEs) throughout the study

Rate and severity of laboratory abnormalities (hematology, biochemistry, urinalysis) throughout the study

- GMT and the geometric mean fold increase in serum antibody titer post-vaccination over Day 1 (baseline) at Days 56 and 224 (Phase 1a) or Days 56 and 168 (Phase 1b):
 - Neutralizing activity against multiple variant spike protein-expressing pseudovirus, and/or PRNT neutralizing activity against wild-type SARS-CoV-2 virus and the variant Beta (B.1.351) in all participants
 - RBD antibody titers against wild-type variant spike protein measured by ELISA
- GMT and the geometric mean fold increase in serum antibody titer post-vaccination over Day 1 (baseline) at Days 7, 28, 35, 56, 112, 224 and 336 (Phase 1a); Days 7, 14, 28, 56, 84, 168 and 336 (Phase 1b)
 - Neutralizing activity against multiple variant spike protein-expressing pseudoviruses, and/or PRNT neutralizing activity against multiple variants of SARS-CoV-2 virus and the variant (B.1.351) in all participants
 - RBD antibody titers against wild-type variant spike protein measured by ELISA

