3 STUDY DESIGN

Overview

The trial will be a phase 1a/1b study, randomized, observer-blind, placebo-controlled.

Description of study parts and groups

Phase 1a

Phase 1a of the study will evaluate the safety, tolerability and immunogenicity of a one-dose or two-dose regimen of the VBI-2902a at the low dose level of 5 µg of S protein or placebo in 60 healthy adults 18 to 54 years of age with no previous clinical or laboratory diagnosis of COVID-19 or SARS-CoV-2 infection and not previously received an experimental or authorized COVID-19 vaccine. Participants will be randomized to three cohorts at a 1:1:1 ratio (2:1 ratio to VBI-2902a or placebo [saline]):

- **Group G1** – 20 participants will receive VBI-2902a at a dose of 5 µg of S protein at Day 1 and placebo at Day 28.

- **Group G2** – 20 participants will receive VBI-2902a at a dose of 5 µg of S protein at Days 1 and 28.
- **Group G3** – 20 participants will receive placebo at Days 1 and 28.

An Independent Data Safety Monitoring Board (DSMB) will review blinded safety data (reactogenicity, adverse events and safety laboratory assessments) at Day 7 after the first vaccination. The second vaccination will only be given if the DSMB confirms that Day 7 safety is acceptable and that stopping rules were not met. The DSMB will further review blinded post-vaccination safety through Day 35, 7 days after the second vaccination and through Day 56, 28 days after the second vaccination. A Study Steering Committee (SSC), comprised of representatives from the study sponsor (not involved in study operations) and external vaccine experts, will review unblinded immunogenicity data 7 days and 28 days after the second vaccination. The study will be unblinded following DSMB review of safety data collected through Day 56.

Phase 1b

Phase 1b of the study will evaluate the safety, tolerability and immunogenicity of a one-dose regimen of VBI-2905a at a 5 µg dose level of S protein in healthy adults (18-54 years) who had been previously vaccinated with mRNA vaccines.

The DSMB will perform an early review of blinded post-vaccination safety data at Day 7 (reactogenicity, AEs and safety laboratory assessments). DSMB will review blinded Day 7 safety data after the first 10 participants in groups G4 and G5 (previously vaccinated). Only after the DSMB confirms that safety is acceptable and that stopping rules were not met will the enrollment in the respective study groups continue to its completion.

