6.3.1.2 AE Summaries

An overview summary of TEAEs including:

- 1) Counts and percentages of subjects
 - a. With any TEAE,
 - b. With any local solicited AEs during 7 days of vaccination dosing,
 - c. With any systemic solicited AEs during 7 days of vaccination dosing,
 - d. With any unsolicited AEs within 28 days of each vaccination dose,
 - e. With any unsolicited MAAEs at Day 56 and 28 days after each vaccination dose,
 - f. With any unsolicited SAEs at Day 56 and 28 days after vaccination dose,
 - g. With any unsolicited AEs leading to discontinuation of study vaccination,
 - h. With any unsolicited AEs leading to study discontinuation,
 - i. With any unsolicited AEs during the study,

j. With any unsolicited SAEs during the study.
will be presented stratified by treatment and age group.

For each type of AE noted in the overall summary point 2 except solicited AEs (2b and 2c), we will additionally produce summaries of the AEs by SOC and PT. Furthermore, summaries of event types 2d, and 2i will be presented for by SOC, PT, and severity (mild/moderate/severe/potentially life threatening).

Solicited AEs will be summarized separately for local AEs, systemic AEs, and fever >38 centigrade as collected on the solicited AEs eCRF pages. These summaries will be presented for each dose separately and cumulatively, will count the number of subjects experiencing at least one solicited AE, and will count the number of subjects experiencing at least one of each of the solicited AEs ordered per the solicited AEs eCRF pages.

Lastly, within the solicited AE by SOC/PT summary, 2-sided, alpha=0.05 Fisher's Exact tests will be performed to assess differences in rates of these adverse events between the treatment groups. No adjustment will be made to account for multiplicity of tests performed.

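### Whole-study AE tables pool blinded follow-up with the period after each phase is unblinded (up to 83% of 336 days), with no split at unblinding

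*SAP*

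**What the plan says.** SAP 6.3.1.2 lists the rows of the overview TEAE table, shown by treatment. Row a is any TEAE, row i is "With any unsolicited AEs during the study" and row j is "With any unsolicited SAEs during the study". Each also gets a SOC/PT table, and row i gets one by severity. Under SAP 6.3.1.1, TEAE observation runs from first dose to last visit, and in the unsolicited AE tables a participant counts once, at the highest grade, in the any-event and preferred-term lines.

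Rows d to f are narrower. Row d covers 28 days after each dose. Rows e and f give MAAEs and SAEs at Day 56 and 28 days after dosing.

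The whole-study rows report declared secondary endpoints. Protocol 10.1.2 has "Rate and severity of unsolicited AEs throughout the study", with matching whole-study endpoints for MAAEs and SAEs. SAP 6.3.1.2 has no whole-study MAAE row.

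On blinding, Protocol 8.7.1 says "Each phase of the study will be unblinded after DSMB review of safety data collected through Day 56". SAP 3 says for Phase 1a: "The study will be unblinded following DSMB review of safety data collected through Day 56". Protocol 4.1 says for Phase 1b: "The study will be unblinded following DSMB and SSC review of safety and immunogenicity data collected through Day 56". Visits go on: "Participants will be followed until the study completion on Day 336".

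**The concern.** The protocol glossary defines observer-blind as neither the participant nor the staff measuring outcomes knowing the assignment. Unsolicited AEs depend on that protection. They are elicited by asking participants how they have felt since receiving the product (Protocol 8.5), and intensity draws on participant report and investigator judgement (Protocol 8.6). If these people learn the allocation partway, reporting and grading can shift in one arm without any vaccine effect.

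The planned rows would not show this. One count per participant over the whole study merges the two periods. Because the highest grade is kept, a grade given after unblinding replaces a lower one given under blinding, so the severity table is exposed as well as the count. With 20 to 27 participants per arm, the result could be a false signal or false reassurance in the longer-term safety tables.

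**Working it through.** **The plan's own figure.** Protocol 4.5 says: "The total study duration for each vaccinated subject (assuming a screening period of 28 days) is 364 days". Screening of 28 days plus follow-up to Day 336 gives 28 + 336 = 364, which agrees.

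**Share of follow-up after unblinding.** The inputs are the end of follow-up at Day 336 (Protocol 4.1) and unblinding no earlier than Day 56 (Protocol 8.7.1, SAP 3). Unblinding is by phase and follows a review, so there is a lag L between a participant's own Day 56 and the unblinding date. The documents do not give L; 0 to 84 days is assumed here.

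Share = (336 − 56 − L) / 336

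| L (days) | Days after unblinding | Share |
|---|---|---|
| 0 | 280 | 83.3% |
| 28 | 252 | 75.0% |
| 56 | 224 | 66.7% |
| 84 | 196 | 58.3% |

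Counting from Day 1, L = 0 gives 280/335 = 83.6%. The blinded period is at least 56/336 = 16.7%.

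**What a reporting shift could do (illustration on assumed inputs).** Take equal true event rates and a reporting ratio k in one arm after unblinding. With s the share above, the pooled rate ratio is (1 − s) + s × k.

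- k = 1.25: 1.21 at L = 0 and 1.15 at L = 84.
- k = 1.5: 0.1667 + 0.8333 × 1.5 = 1.42 at L = 0; 0.4167 + 0.5833 × 1.5 = 1.29 at L = 84.
- k = 2: 1.83 at L = 0 and 1.58 at L = 84.

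For participants with at least one AE, assume a constant rate of 0.10 per 28 days, L = 0 and k = 1.5. There are 56/28 = 2 blinded and 280/28 = 10 later intervals. One arm shows 1 − exp(−0.10 × 12) = 69.9%, the other 1 − exp(−0.10 × (2 + 1.5 × 10)) = 81.7%. The gap is about 12 percentage points, or roughly 3 of 27 participants. At 0.05 per 28 days the figures are 45.1% and 57.3%; at 0.20 they are 90.9% and 96.7%.

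**What the other planned outputs cover.**

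- Phase 1a: the 28-day window after the second dose ends at Day 28 + 28 = 56, within the blinded period.
- Phase 1b: the window ends at about Day 1 + 28 = 29. Rows e and f reach Day 56 for MAAEs and SAEs. Other unsolicited AEs on Days 29–56 have no row of their own.
- The interim report (Protocol 10.6.3, SAP 7) includes safety through Day 56. It omits blinded time after Day 56 and all time after unblinding.
- No planned table shows the period after unblinding alone.

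**The case against.** The strongest reply is that open-label ascertainment is assumed. The documents say that the study or phase is unblinded, not that participants and site assessors are told. Protocol 7.9 says, with no end date, that participants will not be told what they received and that only staff unaware of assignment will do safety evaluations. This stands as a real ambiguity. Protocol 8.7.1 treats early unblinding of some sponsor personnel separately, so phase unblinding reads as wider than that, but it does not say how wide.

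Second, collection may be narrower than the endpoints suggest. Protocol 4.12 and the synopsis limit unsolicited AEs to 28 days after vaccination, with MAAEs and SAEs throughout. Protocol 8.1 and 10.1.2 run to Day 336. On the narrow reading, only MAAEs and SAEs enter from the later period. That shrinks the problem without removing it.

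Third, no formal inference rests on these rows. They are descriptive, and the Fisher tests cover solicited events only. No table by relatedness is specified in SAP 6.3.1.2, so biased causality judgements do not reach these counts. SAEs are defined largely by outcome, so row j is less exposed. All of this stands and limits the weight of the point.

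Four stronger inferences are tempting and fail:

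- **That 83% of follow-up is open-label.** It is a ceiling, since any review lag lowers it, and a share of days is not a share of events or a size of bias.
- **That the periods can never be separated.** The AE listings (SAP 6.3.1.3) would allow a later split; it is simply not prespecified.
- **That Phase 1b Days 29–56 go wholly unreported.** Rows e and f and the Day 56 interim output cover part of them.
- **That primary safety is compromised.** The primary 28-day windows fall before unblinding.

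**Conclusion.** The pooling is real. Rows a, i and j and their derived tables combine blinded follow-up, to at least Day 56, with follow-up after the phase is unblinded, and nothing in the SAP separates the two or says how arm differences should then be read. The later period is up to 83% of 336 days, and still more than half at an assumed 84-day lag.

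The consequence is confined to descriptive secondary safety endpoints. The reporting ratios above are illustrations, and the documents offer no estimate of the bias. Its size depends on whether participants and assessors are in fact unblinded and on which AEs are collected after 28 days. This is a cheap improvement worth making before the final tables are produced; it is not a threat to the primary analysis.

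**What to change.** In SAP 6.3.1.2:

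- Present rows a, i and j, and their SOC/PT and severity tables, in two periods: first dose to the actual unblinding date of the phase, and that date to Day 336. Take the highest grade within each period.
- Add a whole-study MAAE row, split the same way.
- Show participants at risk and person-days by arm in each period.
- Base between-arm statements on the blinded period and label the later one as unblinded. A pooled row may stay as a description.

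Also reconcile two sets of passages: Protocol 7.9 with 8.7.1, on who is unblinded and when; and Protocol 4.12 and the synopsis with 8.1 and 10.1.2, on whether unsolicited AEs that are not medically attended are collected beyond 28 days.

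The cost is a period flag from onset and unblinding dates and a few more tables. No new data are needed. The price is sparser counts in each period.

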7.11 Contraindications to Administration of the Product

The following events constitute contraindications to administration of the study products at that point in time; if any of these events occur at the time scheduled for injection, the participant may be injected at a later date, within the time window specified in the protocol (+/-3 days for Day 28 administration), or withdrawn at the discretion of the investigator.

Acute disease and/or fever at the time of administration. Fever is defined as temperature $\geq 38.0^{\circ}\text{C} / 100.4^{\circ}\text{F}$ oral.

Participants with any signs or symptoms consistent with COVID-19 illness (as described in the [Section 4.2](#)) should not receive the study vaccine.

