^b Induration/Swelling was evaluated and graded using the functional scale as well as the actual measurement. Source: (US Food and Drug Administration 2007)

Table 6: Toxicity Grading Scale for Solicited Systemic Adverse Events

Systemic (General)	Mild (Grade 1)	Moderate (Grade 2)	Severe (Grade 3)	Potentially Life-Threatening (Grade 4)
Nausea/vomiting	No interference with activity or 1-2 episodes/24 hours	Some interference with activity or >2 episodes/24 hours	Prevents daily activity, requires outpatient IV hydration	ER visit or hospitalization for hypotensive shock
Diarrhea	2 - 3 loose stools or < 400 g/24 hours	4 - 5 stools or 400-800 g/24 hours	6 or more watery stools or >800 g/24 hours or requires outpatient IV hydration	ER visit or hospitalization
Headache	No interference with activity	Repeated use of non-narcotic pain reliever >24 hours or some interference with activity	Significant; any use of narcotic pain reliever or prevents daily activity	ER visit or hospitalization
Fatigue	No interference with activity	Some interference with activity	Significant; prevents daily activity	ER visit or hospitalization
Myalgia	No interference with activity	Some interference with activity	Significant; prevents daily activity	ER visit or hospitalization

Abbreviations: ER=emergency room; IV=intravenous Source: (US Food and Drug Administration 2007)

Table 7: Toxicity Grading Scale for Solicited Other Adverse Events

Vital Signs	Mild (Grade 1)	Moderate (Grade 2)	Severe (Grade 3)	Potentially Life-Threatening (Grade 4)
Fever ^a (°C) ** (°F) *	38.0–38.4 100.4–101.1	38.5–38.9 101.2–102.0	39.0–40 102.1–104	>40 >104
Tachycardia – beats/min	101–115	116–130	>130	ER visit or hospitalization for arrhythmia
Bradycardia – beats/min ^b	50–54	45–49	<45	ER visit or hospitalization for arrhythmia
Hypertension (systolic) - mm Hg	141–150	151–155	>155	ER visit or hospitalization for malignant hypertension
Hypertension (diastolic) - mm Hg	91–95	96–100	>100	ER visit or hospitalization for malignant hypertension
Hypotension (systolic) – mm Hg	85–89	80–84	<80	ER visit or hospitalization for hypotensive shock
Respiratory Rate – breaths/min	17–20	21–25	>25	Intubation

Abbreviations: ER=emergency room.

Note: Subject were at rest for all vital sign measurements

^aOral temperature; no recent hot or cold beverages or smoking

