6.3.3 Vital Signs

A summary of vital signs will be presented by visit & time point. Within each dosing visit, change from pre-dose vital signs will also be summarized. The counts of subjects presenting abnormal vital signs by visit and severity will be produced for fever >38 centigrade, tachycardia, bradycardia, and hypertension.

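### The SAP counts fever only above 38 °C, while protocol Table 7 grades it from 38.0 °C; the graded vital-sign counts could also cover hypotension and respiratory rate

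*SAP*

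**What the plan says.** **SAP.** Section 6.3.1.2 summarises solicited events in three blocks: local, systemic, and "fever >38 centigrade as collected on the solicited AEs eCRF pages". Section 6.3.3 then specifies graded counts for abnormal vital signs: "The counts of subjects presenting abnormal vital signs by visit and severity will be produced for fever >38 centigrade, tachycardia, bradycardia, and hypertension". Both places use a strict inequality. SAP Section 7 declares no departure from the protocol's planned analyses.

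**Protocol, Section 8.6.** Table 7, titled "Toxicity Grading Scale for Solicited Other Adverse Events", gives the Grade 1 fever band as "38.0–38.4 100.4–101.1" (°C, then °F). It also grades tachycardia, bradycardia, systolic and diastolic hypertension, "Hypotension (systolic) – mm Hg" and "Respiratory Rate – breaths/min".

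**Protocol, elsewhere.** Section 7.11 lists "Acute disease and/or fever at the time of administration. Fever is defined as temperature" at or above 38.0 °C oral. Sections 6.1.8 and 7.13 set the same limit. Section 6.1.5 and the footnotes to Tables 1 and 2 have temperature, blood pressure, heart rate and respiratory rate measured before and 60 minutes after vaccination.

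**The concern.** Solicited reactions in the 7 days after each dose are the first primary endpoint. Protocol 4.2 names fever among the solicited systemic events, and the SAP reports it as a block of its own. If the counting rule starts above the point where the protocol starts grading, the lowest Grade 1 reading falls out and the fever rate can only go down. The groups are small, so a single participant is visible in the table.

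Section 6.3.3 also promises counts by severity for some of the signs in Table 7 and not for others, and gives no reason for the selection. A reader of the report could not see how many participants reached each grade of low systolic pressure or raised respiratory rate.

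**Working it through.** **1. Does Table 7 include exactly 38.0 °C?** Convert the Fahrenheit limit: (100.4 − 32) × 5/9 = 38.0 °C. The two units agree, so a reading of 38.0 °C is Grade 1.

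**2. Which readings does the SAP rule drop?** Table 7 is written to 0.1 °C. Thermometer resolution is not stated, so 0.1 °C steps are an assumption.

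| Rule | Grade 1 readings counted |
|---|---|
| Table 7, or ≥38.0 °C | 38.0, 38.1, 38.2, 38.3, 38.4 |
| SAP, >38 °C | 38.1, 38.2, 38.3, 38.4 |

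The only difference is 38.0 °C. Grades 2 to 4 begin at 38.5 °C and are the same under both rules.

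**3. Who is lost?** SAP 6.3.1.2 counts participants with at least one event. Someone who reads 38.0 °C one day and 38.3 °C the next is still counted. Only a participant whose highest reading in the window is exactly 38.0 °C is missed.

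**4. What is one such participant worth?** Group sizes are in protocol Table 3.

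- Phase 1a, 20 per group: 1/20 = 5.0 percentage points.
- Phase 1b, 27 per group: 1/27 = 3.7 percentage points.

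The documents give no expected fever rate and no temperature distribution, so the expected number missed cannot be computed.

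**5. How much of Table 7 do the severity counts in SAP 6.3.3 cover?**

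| Table 7 row | Named in SAP 6.3.3 |
|---|---|
| Fever | yes (above 38 °C) |
| Tachycardia | yes |
| Bradycardia | yes |
| Hypertension, systolic | yes |
| Hypertension, diastolic | yes |
| Hypotension, systolic | no |
| Respiratory rate | no |

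Coverage is 5 of 7 rows. The two missing rows have no count at any grade.

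**The case against.** The best defence on fever is that the SAP ties the item to eCRF pages that are not in these documents. The phrase may be a loose label for an eCRF field that is graded by Table 7, and protocol 10.6.2 independently calls for the FDA toxicity scale. This stands as a limit: the undercount follows only if the SAP text is programmed as written. The mismatch in wording exists either way. It is also fair that protocol 6.1.8, 7.11 and 7.13 define fever for operational purposes (rescheduling an injection, recognising prophylactic antipyretics), so Table 7 carries the argument and the others only show consistency.

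On the two missing rows the defence is stronger. No endpoint names vital signs, and Table 7 sits apart from the local and systemic tables. Protocol 10.7.1 asks only that vital signs be tabulated, which the by-visit summary in SAP 6.3.3 does. A graded count goes beyond that requirement.

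A reader might infer that low blood pressure and fast breathing would go unreported. The documents do not support this. The values enter the by-visit summaries (SAP 6.3.3) and the listings of all CRF data (SAP 5.1). Investigators assess out-of-range post-dose values (protocol 7.10), and clinically significant abnormal findings that meet the definition are recorded as adverse events (protocol 8.2).

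A reader might also infer that a fifth or more of Grade 1 fevers would be lost, because 38.0 is one of five values in the band. That is a share of possible readings, not of participants. Turning it into a rate needs a temperature distribution that the documents do not give.

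**Conclusion.** The fever cut-off is wrong as written: two SAP sections exclude a reading that protocol Table 7 grades, and SAP Section 7 does not declare the difference. The effect is confined to participants whose peak is exactly 38.0 °C, each worth 5.0 or 3.7 percentage points of a group's rate. It rests on literal programming of the SAP text and on recording to 0.1 °C. The cut-off is the same in every group. The stopping criterion for fever above 40.0 °C is not touched.

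The absence of graded counts for systolic hypotension and respiratory rate is a gap in presentation, not an error against a specified analysis. Both points are minor and easily settled.

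**What to change.** **Correction.** In SAP 6.3.1.2 and 6.3.3, replace the strict cut-off with ≥38.0 °C, graded by protocol Table 7. Check that the eCRF fever item uses the same limit. If it does not, derive the count from the recorded temperatures where they are held, or state and justify the difference in SAP Section 7.

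**Improvement.** Add systolic hypotension and respiratory rate to the severity counts in SAP 6.3.3, using the Table 7 grades. This takes coverage from 5 to 7 of the 7 rows.

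**Cost.** Two wording changes, two parameters added to one table, and one check of the eCRF. No new data are needed, and neither the protocol nor the care of participants changes. The one uncertainty is how the eCRF stores temperature. If it holds only a yes/no flag set above 38 °C, readings of exactly 38.0 °C would have to be taken from the diary cards, which are source documents under protocol 6.1.15.
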